1 STUDY OVERVIEW

1.1 BACKGROUND/INTRODUCTION:

Endoscopic retrograde cholangiopancreatography (ERCP) is an invasive diagnostic and therapeutic procedure associated with a risk of serious complications, the most common of which is post-ERCP pancreatitis (PEP). Despite the implementation of various prophylactic measures, as for example those issued in the guidelines of the European (ESGE) and American (ASGE) Societies of Gastrointestinal Endoscopy, the occurrence of PEP remains a clinically significant issue. The aim of this study is to assess the incidence of PEP and to analyze the implementation of prophylactic measures in routine clinical practice.

1.2 STUDY DESIGN

- **Study type:** Prospective, observational, multicenter study.
- **Duration:** The study will be terminated when the required number of patients will be reached. Estimated end of data collection is May 31, 2026
- **Location:** Selected centers within the Slovakia and Czechia. The centers selected for this study are those that expressed interest in participating based on our yet unpublished survey, conducted between January and June 2024, which aimed to assess how ERCP quality parameters were monitored and how prophylactic measures for PEP were implemented across centers. A total of 26 ERCP centers participated in the survey, including 14 from Slovakia and 12 from Czechia. Centers that expressed interest, as well as all remaining ERCP-performing centers in Slovakia and several in Czechia, were subsequently contacted by email with information about the study and invited to participate.

1.3 PRIMARY AIM

- To determine the incidence of PEP (any severity) in real clinical practice at selected ERCP centers in the Slovakia and Czechia.

1.4 SECONDARY AIMS

- To determine the incidence of PEP across different severity grades: none, mild, moderate, and severe.
- To evaluate the use of preventive measures for prevention of PEP in real clinical practice at selected ERCP centers in Slovakia and Czechia.
- To investigate association between the incidence of PEP and the use of measures of prevention.
- To assess PEP-related mortality.

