3.2 SECONDARY OUTCOMES

Outcome	Obtained data in each enrolled patient
Incidence of different severity grades of PEP	Severity of PEP (none/mild/moderate/severe) *(as detailed below)
Rate of use of PEP preventive measures	
Patients estimated risk of PEP: low/high **(as detailed below)
 
Prophylactic Measures Considered “Adequate” per ESGE
 
a) Low-risk patients
 
 • NSAID administration (preferred) • Aggressive hydration if NSAIDs contraindicated • Nitroglycerin if both NSAIDs and aggressive hydration are contraindicated + consider Prophylactic Pancreatic Stent (PPS) ***(as detailed below) 
b) High-risk patients
 
 • NSAID + PPS***(as detailed below) • Aggressive hydration + PPS***(as detailed below) if NSAIDs contraindicated • Nitroglycerin + PPS***(as detailed below) if both NSAIDs and aggressive hydration are contraindicated
Determination and/or confirmation of PEP risk factors	Age, sex, indication for ERCP, and patient-related and procedure-related risk factors according to ESGE **(as detailed below)

3.2.1 * Severity Grading of PEP (Atlanta-based criteria)

Mild PEP- without organ failure and local or systemic complications

Moderate PEP- with transient organ failure that resolved within 48 hours and/or local or systemic complications (see below)

Severe PEP- with persistent organ failure (see below)

Local complications:

- Acute peripancreatic fluid collection
- Pancreatic pseudocyst
- Acute necrotic collection
- Walled-off necrosis (WON)
- Gastric outlet dysfunction
- Portal or splenic vein thrombosis
- Necrosis of the colon

Systemic complications

- Exacerbation of chronic disease (e.g., heart failure or chronic obstructive pulmonary disease)

Organ failure

- Respiratory failure with hypoxemia
- Cardiovascular failure with hypotension
- Renal failure

3.2.2 ** Determination of PEP risk

High risk for developing PEP is defined as:

- a) the presence of at least one definite risk factor (see below), or
- b) the presence of two or more probable risk factors (see below).

Risk factors for the development of PEP according to ESGE:

Definite risk factors

- Suspected SOD (Sphincter of Oddi Dysfunction)
- Female sex
- History of acute pancreatitis
- History of PEP
- Difficult cannulation

Probable risk factors

- Age less than 35 years
- Normal serum bilirubin level
- Non-dilated bile ducts
- Absence of chronic pancreatitis
- End-stage kidney disease
- Precut

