4.2 PRIMARY OUTCOME

For the primary outcome, the rate of PEP will be calculated along with 95% confidence interval obtained using the Wilson method.

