4.3 SECONDARY OUTCOMES

The rates of use of different preventive measures will be listed for all patients and separated by the patients PEP risk level. Point estimates along with two-sided 95% confidence intervals will be provided.

A logistic regression model will be used to estimate the influence of preventive measures on the risk of PEP controlling for patients PEP risk.

For each risk factor, a separate logistic regression model will be used to estimate the risk of PEP. Risk factors with a statistically significant result in their single-variable model will be included into a single multi-variable model.

Additional post-hoc tests may be performed.

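### Does the secondary aim on PEP-related mortality need its own outcome row, denominator and interval method in the SAP?

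*SAP*

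**What the plan says.** Section 1.4 of the SAP has four secondary aims: severity grades, use of preventive measures, the association between those measures and PEP, and "To assess PEP-related mortality".

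The table in section 3.2 has three rows: "Incidence of different severity grades of PEP", "Rate of use of PEP preventive measures" and "Determination and/or confirmation of PEP risk factors". None of them is death, and the severity scale stops at persistent organ failure.

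Section 4.3 begins with "The rates of use of different preventive measures will be listed for all patients", with 95% intervals. It then describes a logistic model for preventive measures and, for risk factors, "For each risk factor, a separate logistic regression model will be used to estimate the risk of PEP". It closes with "Additional post-hoc tests may be performed".

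The interval method is stated once, in section 4.2: "For the primary outcome, the rate of PEP will be calculated along with 95% confidence interval obtained using the Wilson method". Section 4.4 makes an estimate with a two-sided 95% interval the preferred presentation for most results and declares every secondary outcome exploratory.

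**The concern.** A SAP should carry each stated aim through to an outcome and an analysis. Here the lists do not match. Mortality is in 1.4 alone. Severity is in 1.4 and 3.2 without a line in 4.3. Risk factors are in 3.2 and 4.3 but are not an aim in 1.4. Mortality is the only aim with neither an outcome row nor a named analysis.

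Deaths from PEP may be very few, and interval methods differ most at small counts. If an analyst used the Wald formula and no deaths occurred, the report would show 0% with limits of 0 and 0, which reads as certainty. The denominator is also open: all enrolled patients, or only those who developed PEP. Leaving both choices until the data are known would allow the more favourable presentation to be picked.

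**Working it through.** **Inputs.** From SAP 4.2.1: 950 evaluable patients, 1000 enrolled, PEP rate up to 15%, margin 2.5 points, 90% probability. Assumed, because the SAP gives no mortality rate: 0 or 1 death, and a PEP rate of 5% as a lower case. PEP cases: 0.15 × 950 = 142.5 (143) and 0.05 × 950 = 47.5 (48).

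**Step 1: the SAP's own figure.** Following 4.2.1, sum the Binomial(n, 0.15) probabilities over all outcomes whose farther 95% limit lies within 2.5 points of the estimate.

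| Interval | Probability at n = 950 | Smallest n reaching 90% |
|---|---|---|
| Wilson | 91.2% | 946 |
| Wald | 99.97% | 851 |
| Clopper-Pearson | 84.1% | 960 |

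Of the three, only Wilson fits the stated 950 and 90%. The target of 1000 corresponds to 950 / 0.95, a 5% loss that the SAP does not state.

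**Step 2: formulas for mortality.** With p = x/n and z = 1.96 (z² = 3.8415):

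- Wald: p ± z√(p(1−p)/n). At x = 0 this is 0 to 0 for any n.
- Wilson: [p + z²/(2n) ± z√(p(1−p)/n + z²/(4n²))] / (1 + z²/n). At x = 0 the upper limit is z²/(n + z²).

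At x = 0, Wilson gives 3.8415/953.84 = 0.403% (n = 950), 3.8415/146.84 = 2.616% (n = 143) and 3.8415/51.84 = 7.410% (n = 48).

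**Step 3: upper 95% limits by method and denominator.**

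| Deaths / n | Wilson | Clopper-Pearson | Jeffreys | Wald |
|---|---|---|---|---|
| 0 / 950 | 0.403% | 0.388% | 0.264% | 0% |
| 1 / 950 | 0.594% | 0.585% | 0.491% | 0.311% |
| 0 / 143 | 2.616% | 2.547% | 1.738% | 0% |
| 1 / 143 | 3.855% | 3.835% | 3.221% | 2.065% |

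Wald also gives negative lower limits at 1 death: −0.101% of 950 and −0.667% of 143.

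**Step 4: what drives the difference.**

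- Wilson against exact at 0/950: 0.403 − 0.388 = 0.015 points.
- Wilson against Jeffreys at 0/950: 0.264/0.403 = 0.66, so Jeffreys is about a third lower. Wald is therefore not the only method that departs from Wilson, although it is the only one of these with zero width at 0 deaths.
- 950 patients against 143 PEP cases, both Wilson at 0 deaths: 2.616/0.403 = 6.5-fold. Against 48 cases: 7.410/0.403 = 18-fold.

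The denominator matters far more than the choice between Wilson and exact. But the two denominators answer different questions: the risk of fatal PEP per patient enrolled, and the fatality among PEP cases. Given the death count, the number enrolled and the number of PEP cases, a reader can form either.

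**The case for a change.** The strongest case for a change is that aims, outcomes and analyses all belong to this one document, so the mismatch cannot be put down to an unseen protocol. The general rule in 4.4 names neither a method nor a denominator for deaths, and a few lines of wording would settle both before data are seen.

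The textual part stands: mortality does not appear after 1.4. The consequence is weaker. The misleading 0 to 0% result needs an analyst to drop the one method the SAP names in favour of one that does not fit its own sample size, and nothing in the SAP points that way.

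The permission for further tests in 4.3 does not make mortality post hoc. It is declared in advance in 1.4, and a descriptive proportion is not an additional test. Since every secondary outcome is exploratory, the label would carry little inferential weight anyway.

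How a PEP-related death is defined, over what period, and on which form it is recorded are matters a protocol commonly settles. Section 3 here covers only PEP occurrence and severity up to discharge, and the protocol and case report form are not at hand. It therefore cannot be said that death is not collected, nor that adding a row would cost nothing.

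The other mismatches are matters of tidiness. Severity has defined grades recorded for each enrolled patient, so a count and percentage per grade follows without further instruction. Risk factors have both an outcome row and an analysis.

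**Conclusion.** No change to the plan follows. The missing mortality line is an editorial gap that analysts would fill sensibly: a count, and a proportion with the Wilson interval already used for PEP. No rule that the SAP states gives a wrong result.

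With 0 deaths that interval reaches 0.40% of 950 patients, or about 2.6% of 143 PEP cases; the exact method gives 0.39% and 2.5%. The 6.5-fold difference between the denominators is one between two quantities, not an ambiguity in either, and is visible once both totals are reported. The primary estimate, its interval and the sample size of 950 (1000 with losses) are untouched.

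This rests on three assumptions: 0 or 1 death, 143 PEP cases (the SAP's 15% planning ceiling), and analysts carrying Wilson over to secondary proportions. If a Wald interval were used after all, the 0 to 0% result would be a real reporting fault, but one plain to any reader of the report.

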2 STUDY POPULATION

2.1 INCLUSION CRITERIA

- ERCP in a patient with a native papilla (first ERCP) or repeat ERCP in a patient with previous failed cannulation attempt.
- Age at least 18 years at the time of ERCP.
- Signed informed consent.

2.2 EXCLUSION CRITERIA

- Previous papillotomy, papilla dilation, or sphincteroplasty.
- Rendez-vous cannulation technique.
- ERCP not performed due to insufficient patient cooperation.
- ERCP terminated before cannulation due to sedation/anesthesia-related complications.
- Failure to reach the Vater's or minor papilla (e.g. duodenal stenosis).
- Acute biliary pancreatitis.
- Altered anatomy that prevents reaching the papilla with a standard duodenoscope (e.g. Roux-en-Y).

3 DATA COLLECTION AND OUTCOMES

Form of collection: Paper case report forms (CRF), filled out at the time of the procedure by the attending physician.

Recording occurrence of PEP: Within 24-48 hours after the procedure.

Monitoring PEP severity: Every 7 days until hospital discharge.

3.1 PRIMARY OUTCOME

Outcome	Obtained data
Incidence of PEP	Presence/absence of PEP (any severity) in each enrolled patient.

3.2 SECONDARY OUTCOMES

Outcome	Obtained data in each enrolled patient
Incidence of different severity grades of PEP	Severity of PEP (none/mild/moderate/severe) *(as detailed below)
Rate of use of PEP preventive measures	
Patients estimated risk of PEP: low/high **(as detailed below)
 
Prophylactic Measures Considered “Adequate” per ESGE
 
a) Low-risk patients
 
 • NSAID administration (preferred) • Aggressive hydration if NSAIDs contraindicated • Nitroglycerin if both NSAIDs and aggressive hydration are contraindicated + consider Prophylactic Pancreatic Stent (PPS) ***(as detailed below) 
b) High-risk patients
 
 • NSAID + PPS***(as detailed below) • Aggressive hydration + PPS***(as detailed below) if NSAIDs contraindicated • Nitroglycerin + PPS***(as detailed below) if both NSAIDs and aggressive hydration are contraindicated
Determination and/or confirmation of PEP risk factors	Age, sex, indication for ERCP, and patient-related and procedure-related risk factors according to ESGE **(as detailed below)

3.2.1 * Severity Grading of PEP (Atlanta-based criteria)

Mild PEP- without organ failure and local or systemic complications

Moderate PEP- with transient organ failure that resolved within 48 hours and/or local or systemic complications (see below)

Severe PEP- with persistent organ failure (see below)

Local complications:

- Acute peripancreatic fluid collection
- Pancreatic pseudocyst
- Acute necrotic collection
- Walled-off necrosis (WON)
- Gastric outlet dysfunction
- Portal or splenic vein thrombosis
- Necrosis of the colon

Systemic complications

- Exacerbation of chronic disease (e.g., heart failure or chronic obstructive pulmonary disease)

Organ failure

- Respiratory failure with hypoxemia
- Cardiovascular failure with hypotension
- Renal failure

3.2.2 ** Determination of PEP risk

High risk for developing PEP is defined as:

- a) the presence of at least one definite risk factor (see below), or
- b) the presence of two or more probable risk factors (see below).

Risk factors for the development of PEP according to ESGE:

Definite risk factors

- Suspected SOD (Sphincter of Oddi Dysfunction)
- Female sex
- History of acute pancreatitis
- History of PEP
- Difficult cannulation

Probable risk factors

- Age less than 35 years
- Normal serum bilirubin level
- Non-dilated bile ducts
- Absence of chronic pancreatitis
- End-stage kidney disease
- Precut
- Pancreatic sphincterotomy
- Papilla dilation without sphincterotomy
- Failure to completely remove stones from bile ducts

3.2.3 *** Placement of a PPS

Placement of a PPS is recommended, provided there is good access to the pancreatic duct.

4 PLANNED ANALYSES

4.1 CHARACTERISTICS OF PATIENTS AND PROCEDURES

The following characteristics of **patients** will be summarized as mean with standard deviations, medians with quartiles or as counts with percentages:

- Age
- Gender
- **Patient-related risk factors of post-ERCP pancreatitis (PEP)**
 - History of acute pancreatitis
 - History of PEP
 - Normal bilirubin
 - Nondilated bile ducts
 - Dilated pancreatic duct
 - Chronic pancreatitis
 - Peripapillary diverticulum
 - End-stage renal disease

The following characteristics of **procedures** will be summarized as mean with standard deviations, medians with quartiles or as counts with percentages:

- Difficult cannulation (more than 5 minutes, more than 5 contacts, more than 1 unintended pancreatic duct cannulation or opacification)
- Guidewire-assisted cannulation
- Contrast-assisted cannulation
- Conventional precut (starting at the upper margin of the papillary orifice)
- Precut- fistulotomy
- Dual-wire cannulation (pancreatic guidewire-assisted biliary cannulation)
- Trans-pancreatic biliary sphincterotomy
- Biliary sphincterotomy
- Pancreatic sphincterotomy
- Papillary balloon dilation (without previous sphincterotomy)
- Papillary large balloon dilation (after sphincterotomy)
- Pancreatic duct brushing cytology
- Minor papilla cannulation
- Failed cannulation (cannulation of the desired duct was not successful)
- Was the procedure effective? (Was the intended goal achieved?)
- Cholangioscopy or pancreaticoscopy
- EUS plus ERCP (during one session)
- Was a trainee involved? (Did trainee participate in the cannulation?)

4.2 PRIMARY OUTCOME

For the primary outcome, the rate of PEP will be calculated along with 95% confidence interval obtained using the Wilson method.

4.2.1 Sample size calculation

When assuming the rate of PEP being up to 15 %, the study with 950 participants will have 90 % power to provide a two-sided 95% confidence interval for the PEP rate within a 2.5 % (absolute) margin on either side of the point estimate. To account for an expected drop-out (due to data issues), the final target sample size was set to 1000 patients.

The sample size calculation was performed as follows: Since the required sample size increases with the actual rate of PEP, a simulation using the rate of 15% was performed. For a given sample size, each possible outcome was tested and the error (the larger distance from one side of the confidence interval to the point estimate) was compared to 2.5% and the result was weighted by the probability of obtaining this number of cases (taken from a binomial distribution).

4.3 SECONDARY OUTCOMES

The rates of use of different preventive measures will be listed for all patients and separated by the patients PEP risk level. Point estimates along with two-sided 95% confidence intervals will be provided.

A logistic regression model will be used to estimate the influence of preventive measures on the risk of PEP controlling for patients PEP risk.

For each risk factor, a separate logistic regression model will be used to estimate the risk of PEP. Risk factors with a statistically significant result in their single-variable model will be included into a single multi-variable model.

Additional post-hoc tests may be performed.

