4.4 ALPHA LEVELS AND MULTIPLE TESTING

The study has a pre-defined primary outcome, for which the alpha error level is maintained. There are no pre-defined strategies for multiple testing corrections, and all the secondary outcomes are to be considered as exploratory.

The primary outcome will be presented as a point estimate along with a two-sided 95% confidence interval and this will be the preferred way of presentation for most of the results.

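### The SAP 4.3 model linking preventive measures to PEP has no centre term, so in this non-randomised multicentre study its odds ratio may mix the measure with the centre

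*SAP*

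**What the plan says.** SAP 1.2 describes a "Prospective, observational, multicenter study" in Slovakia and Czechia. It does not give the final number of centres. The only count is for the preceding survey: "A total of 26 ERCP centers participated in the survey, including 14 from Slovakia and 12 from Czechia".

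SAP 1.4 lists as a secondary aim: "To investigate association between the incidence of PEP and the use of measures of prevention".

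SAP 4.3 gives the whole analysis for that aim in one sentence: "A logistic regression model will be used to estimate the influence of preventive measures on the risk of PEP controlling for patients PEP risk". The adjusting variable is defined in SAP 3.2 as "Patients estimated risk of PEP: low/high". No centre or country term, random effect or clustered variance appears anywhere in section 4. The risk-factor models in 4.3 are separate and do not feed this one.

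SAP 4.4, on alpha and multiple testing, adds that "all the secondary outcomes are to be considered as exploratory".

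**The concern.** Which patient receives which measure depends partly on local practice. A centre may use a measure often and also have a higher or lower PEP risk for reasons that low/high does not capture, such as case mix, operator experience or how completely PEP is detected. Pooling such centres without a centre term attributes part of the centre difference to the measure. A measure with no effect can then look protective or harmful, and more patients would not cure this.

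At stake is a named secondary aim. The SAP is where the adjustment set is fixed, and an adjustment for centre chosen after the results are known would carry less weight than a planned one.

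**Working it through.** **The plan's own figure.** The only sample-size figure is 950, for the primary outcome. Following SAP 4.2.1, each possible count x is weighted by Binomial(n, 0.15), and the larger distance from a Wilson limit to x/n is compared with 0.025. The probability of meeting the margin is 0.912 at n = 950, and the smallest n reaching 0.90 is 946. The figure reproduces. It says nothing about the 4.3 model.

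**Inputs for the check**

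- From the SAP: 950 patients; logistic model of PEP on the measure and low/high risk.
- Assumed, because the SAP gives none of these:
  - true OR 1; 10, 20 or 30 centres of unequal size; realised PEP 11-16%;
  - 60% of patients high risk, with OR 2 for high against low;
  - a measure used by about two thirds, between-centre logit SD of use 1.0;
  - between-centre logit SD of PEP risk σ = 0.18 or 0.4, and correlation ρ with use of -0.5, 0 or 0.5.
- On the latent scale, ICC = σ²/(σ² + π²/3). This gives 0.0324/3.322 = 0.010 and 0.16/3.450 = 0.046.

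**Approximate bias by hand.** Let q be a centre's probability of use and z its standardised use effect. Omitting centre shifts the log OR by about ρ·σ·Cov(t, z)/Var(t), where t is receipt of the measure. With SD of use 1, Cov(t, z) = E[q(1-q)] = 0.186 when average use is 2/3, and Var(t) = (2/3)(1/3) = 0.222. The ratio is 0.838.

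- σ = 0.4: 0.5 × 0.4 × 0.838 = 0.168, so OR = exp(∓0.168) = 0.85 or 1.18.
- σ = 0.18: 0.5 × 0.18 × 0.838 = 0.075, so OR = exp(∓0.075) = 0.93 or 1.08.
- ρ = 0: no shift.

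**Simulation** (2,500 runs per setting with 20 centres, 1,500 with 10 and 30; ranges in the no-centre column, and for fixed centres at σ = 0.4, also cover repeat runs of 600 per setting). Median OR, with false positives at the 5% level:

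| Setting | No centre (as planned) | Random intercept only | Fixed centres |
|---|---|---|---|
| σ = 0.4, ρ = ±0.5 | 0.85-0.88 or 1.14-1.17; 12-17% | 0.90-0.95 or 1.07-1.11; 5-8% | 0.98-1.03; 4-6% |
| σ = 0.18, ρ = ±0.5 | about 0.93 or 1.07-1.09; 5-8% | 0.94-0.95 or 1.05-1.06 | 0.99-1.01 |
| σ = 0.4, ρ = 0 | 0.99-1.01; 6-8% | | |

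A measure used by about 10% (20 centres) gave 0.85-0.94 or 1.07-1.17 without centre and 0.98-1.01 with fixed centres.

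**Bias against standard error.** SE of the log OR ≈ 1/√[n·p(1-p)·f(1-f)], with p = 0.13 and f the proportion given the measure.

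- f = 2/3: 1/√(950 × 0.1131 × 0.2222) = 0.205. Largest bias |ln 0.85| = 0.163, or 0.79 SE.
- f = 0.10: 1/√(950 × 0.1131 × 0.09) = 0.32. The same bias is 0.51 SE.

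A shift of 0.79 SE alone gives P(|Z + 0.79| > 1.96) = 0.125, in line with the lower end of 12-17%.

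**What centre adjustment does not do.** An unmeasured patient trait was added, with logit effect 0.5 on both use and PEP and true OR 1. The OR was 1.05-1.41 without centre, 1.14-1.35 with a random intercept and 1.26-1.27 with fixed centres. Where the two biases oppose each other, the model without centre is nearest the truth: 1.05, against 1.14 (random intercept) and 1.26 (fixed centres).

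**The case against.** The strongest case against is that nothing in the SAP shows centres to differ in the required way. The number of centres, both spreads and the correlation are all assumed. The bias is below one standard error, the analysis is exploratory, and SAP 4.3 allows further post-hoc tests. Measures are chosen by patient risk, so confounding by indication within centres is at least as plausible, and a centre term does not touch it and may make the estimate worse. All of this stands, and it limits the priority. It does not remove the point: the exploratory label deals with multiplicity, not bias, and naming the adjustment beforehand costs little.

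Four stronger readings are tempting and are not supported.

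- *The planned OR is biased.* The documents leave the possibility open. They do not show it, and at correlation 0 there is no bias.
- *The low/high class is itself a defect.* It is coarse: a patient is high risk with "the presence of at least one definite risk factor (see below), or" with two probable ones, and female sex alone qualifies. But the class is the plan's stated risk definition. It matters here only because it leaves room for centre differences that the model does not capture.
- *The word influence in 4.3 is a causal claim.* SAP 1.4 already sets the aim as association, so this is wording.
- *A random intercept would settle it.* The table shows that it leaves much of the bias.

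**Conclusion.** The point holds as a cheap improvement of modest priority. SAP 4.3 fixes a model that cannot separate a measure from the centres that use it, in a design where that separation is not guaranteed.

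Under the assumed settings, a null measure would show an OR about 12-17% from 1 with 12-17% false positives at a between-centre SD of 0.4, and about 7-9% from 1 with 5-8% false positives at 0.18. Both rest on a correlation of 0.5 between centre use and centre risk. The bias stays below one standard error of the log OR: about 0.2 for a commonly used measure, about 0.3 for one used by about 10%.

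The PEP rate with its Wilson interval and the sample size are untouched.

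**What to change.** In SAP 4.3, replace the sentence on preventive measures with text such as:

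> The association between preventive measures and PEP will be estimated by logistic regression with terms for PEP risk (low/high) and centre. Centre will enter as fixed effects. The model without centre will be reported alongside. Confounding by indication within centres may remain, and centre adjustment can move the odds ratio further from the truth when the two biases oppose each other. Results will be read as associations.

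An acceptable alternative to fixed effects is a random intercept together with the centre's proportion of patients given the measure, which separates within-centre from between-centre differences. This variant was not simulated here. One of the two should be named in advance.

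Cost: a few sentences and one more model, with no extra patients. The SAP does not list centre among the recorded items, so its availability for every patient is an assumption, though a safe one. In the simulation, fixed centres raised the standard error of the log OR by 9-14% for a commonly used measure and 7-8% for one used by about 10%. Centres with no PEP events drop out of the fixed-effects model: on average about 0.2 of 10, 1-2 of 20 and 3 of 30. The number dropped should be reported.
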